9 PHARMACOKINETIC AND BIOMARKER SUMMARIES

All PK and biomarker analyses are outside of the scope of this statistical analysis plan.

10 IDENTIFICATION AND SUMMARY OF PROTOCOL DEVIATIONS

In accordance with ICH E3 guidelines, protocol deviations will be presented. A listing of subjects who were randomized and failed to meet one or more eligibility criteria will be provided. Eligibility deviations will also be summarized by the inclusion/exclusion criteria violated by a subject.

In addition important post-randomization protocol deviations will be summarized as a cross tabulation of the deviation code and categories identified below:

Deviation code:

- Did Not Satisfy Inclusion or Exclusion Criteria
- Prohibited Medication
- Treatment Deviation
- Withdrawal Deviation
- Randomization Irregularity
- Other Protocol Deviation

Deviations category:

- IMPORTANT
 - Potentially Impacting Safety
 - ➤ Potentially Impacting Efficacy
 - ➤ Potentially Impacting Safety and Efficacy
 - > Other Potential Impact
- OTHER

11 DATA QUALITY ASSURANCE

The Clinical, Data Management, Biostatistics, and Medical Writing departments at Exelixis and designees will work diligently and collaboratively to ensure that the data collected and analyzed for this study are of the highest quality. Controls including Case Report Form (CRF) design, CRF annotation, database design, data-entry processes, data validation programs, discrepancy management, consistent use of medical coding, data extraction processes, and database locking processes ensure the quality of the data. These controls are assessed at regular intervals during a trial.

In addition to electronic evaluation of the data and verification of data from source documents at the respective sites, a data review meeting will be held to review the data and correct significant data anomalies before the study database is locked or data are extracted for the purpose of analysis.

Appendix A: Date Imputation Rules

Incomplete Cancer Diagnosis Date

If year is missing (or completely missing): do not impute

If only day is missing: set to 15th of the month.

If day and month are missing: set to July 1st.

If either imputation rule above results in a diagnosis date > informed consent: set diagnosis date to the date of informed consent - 1.

Incomplete Adverse Event Onset Date

Assumption: For on-study Adverse Events.

If *year* is missing (or completely missing): set to the date of first dose.

If (year is present and month and day are missing) or (year and day are present and month is missing):

If *year* = year of first dose: set the date to the first dose date.

If year < year of first dose: set month and day to December 31st.

If year > year of first dose: set month and day to January 1st.

If *month* and *year* are present and *day* is missing:

If *year* = year of first dose, and:

If *month* = month of first dose: set *day* to day of first dose.

If *month* < month of first dose: set *day* to last day of *month*.

If month > month of first dose: set day to 1st day of month.

If year < year of first dose: set day to last day of month.

If year > year of first dose: set day to 1^{st} day of month.

For all other cases: set to date of first dose.

Incomplete Prior and Concomitant Medication*, Radiation, Surgery/Procedure Start Date

If *year* is missing (or completely missing): do not impute.

If (year is present and month and day are missing) or (year and day are present and month is missing):

Set month and day to January 1st.

If year and month are present and day is missing:

Set day to 1st day of month.

Incomplete Prior and Concomitant Medication*, Radiation, Surgery/Procedure End Date

If year is missing (or completely missing): do not impute.

If (year is present and month and day are missing) or (year and day are present and month is missing):

Set *month* and day to December 31st.

If *year* and *month* are present and *day* is missing:

Set day to last day of the month.

* Including prior and concomitant medications, transfusions and Opioid pain medication record

Incomplete Subsequent Anti-Cancer Therapy* Start Date

Assumption: Anti-Cancer therapies reported on the Subsequent Anti-Cancer Therapy CRF.

If year is missing (or completely missing): set to date of last dose of study treatment + 1

If (year is present and month and day are missing) or (year and day are present and month is missing):

If year > year of the last dose: Set *month* and day to January 1st.

If year = year of the last dose: Set month and day to last dose date of study treatment + 1

If *year* and *month* are present and *day* is missing:

Set day to 1st day of month if the resulting imputed date is greater than date of last dose. Otherwise set the imputed date to date of last dose + 1

* Including concomitant and subsequent anti-cancer therapy, surgeries and procedures, and radiation, radionuclides & radiotracers.

Incomplete Study Treatment Start Date

Define previous sequential dosing "milestone" as the latest of previous dose stop date, previous dose hold stop date, date of first dose or randomization date. If *year* is missing (or completely missing): set to date of previous sequential dosing "milestone" + 1

If (year is present and month and day are missing) or (year and day are present and month is missing): set to January 1st

If year and month are present and day is missing: set to the first day of the month

If the imputed date is before the previous sequential dosing "milestone": set to the date of previous sequential dosing "milestone" + 1

Incomplete Study Treatment Stop Date

Define next sequential dosing "milestone" as the earliest of next dose start date, next dose hold start date, date of last dose from EOT CRF or the cutoff date.

If year is missing (or completely missing): set to date of next sequential dosing "milestone" - 1

If (year is present and month and day are missing) or (year and day are present and month is missing): set to December 31st

If year and month are present and day is missing: set to the last day of the month

If the imputed date is after the next sequential dosing "milestone": set to the date of next sequential dosing "milestone" -1

Incomplete Death Date

Identify date of last known alive (LA) prior to death from the following:

- 1. Date of decision to discontinue study treatment from End of Treatment CRF
- 2. Date of last radiographic assessment from End of Radiographic Follow Up CRF
- 3. Date last known alive from Survival Follow Up CRF
- 4. Date of last lab assessment from the Labs dataset

If year is missing (or completely missing): set to date of LA + 1

If only day is missing: set to the maximum of the first of month or LA + 1

If month and day are missing:

If year of LA = year of death

Set death date to date of LA + 1

If year of most-recent contact < year of death

Set month and day to Jan 1st

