## 4.3 Exclusion Criteria:

- 1. The subject has previously received cabozantinib.
- 2. The subject has received prior treatment with a small molecule kinase inhibitor or a hormonal therapy (including investigational kinase inhibitors or hormones) within 28 days or five half-lives of the compound or active metabolites, whichever is shorter before randomization or at any time after the date of the qualifying images used to document PD for eligibility
- 3. The subject has received prior systemic anti-tumor therapy (eg, chemotherapy, biologic modifiers, or anti-angiogenic therapy) within 28 days of randomization (42 days [6 weeks] for nitrosoureas or/mitomycin C) or at any time after the date of the qualifying images used to document PD for eligibility
- 4. The subject has received any other type of investigational agent within 28 days before randomization or at any time after the date of the qualifying images used to document PD for eligibility
- 5. The subject has received radiation therapy within 28 days (14 days for radiation for bone metastases) or radionuclide treatment (eg, I-131 or Y-90) within 42 days (6 weeks) of randomization. Subject is ineligible if there are any clinically relevant ongoing complications from prior radiation therapy
- 6. The subject has untreated and/or active (progressing or requiring anticonvulsants or corticosteroids for symptomatic control) central nervous system (CNS) metastasis. Must have completed radiation therapy ≥ 28 days prior to randomization and stable without corticosteroids or anti-convulsant treatment for ≥ 10 days
- 7. Concomitant anticoagulation at therapeutic doses with oral anticoagulants (eg, warfarin, direct thrombin and factor Xa inhibitors) or platelet inhibitors (eg, clopidogrel).
  Note: Low-dose aspirin for cardioprotection (per local applicable guidelines), low-dose warfarin (< 1 mg/day), and low dose low molecular weight heparins (LMWH) are permitted. Anticoagulation with therapeutic doses of LMWH is allowed in subjects without radiographic evidence of brain metastasis, who are on a stable dose of LMWH for at least 12 weeks before randomization, and who have had no complications from a thromboembolic event or the anticoagulation regimen.

- 8. The subject has uncontrolled, significant intercurrent or recent illness including, but not limited to, the following conditions:
  - a. Cardiovascular disorders including

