4.6 Definition of Prior, Concomitant, and Subsequent Therapy

For the purpose of inclusion in prior and/or concomitant medication tables, incomplete medication/therapy start and stop dates will be imputed as detailed in Appendix A. Based on imputed start and stop dates:

- Prior medications/radiation therapies are defined as medications with a start/stop date occurring before the date of first dose of study treatment.
- Concomitant medications/radiation therapies are defined as medications that stop or continue on or after date of first dose day through the end of safety observation period.
- Concomitant and Subsequent non-radiation anticancer therapies/radiation therapies are defined as those that stop or continue on or after the date of randomization.

Medications/radiation therapies may be summarized as prior, concomitant and/or subsequent.

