7.1.3 Primary Analysis

The primary efficacy analysis of PFS will include all subjects in the ITT population and will evaluate whether PFS for subjects in the 60 mg cabozantinib arm is non-inferior to PFS in subjects in the 140 mg cabozantinib arm. The primary efficacy analysis is event based and will be conducted when at least 150 PFS events have been observed.

The recorded date of radiographic progression is the date of the tumor assessment visit at which progression is declared per IRC per RECIST 1.1. If multiple scan dates are associated with a tumor assessment visit, the earliest assessment date within the set will be chosen as the progression date.

Only adequate tumor assessments (ATAs) will be considered in the determination of radiographic progression and censoring dates. For the purpose of this study, ATA is defined as one that results in a time point assignment of: response (complete or partial), stable disease/(non-

CR, non-PD), or progression. For PFS, ATA is based on soft tissue evaluation by CT/MRI.

Single missing or inadequate scheduled tumor assessments will be ignored. No values will be imputed.

The censoring rules shown in Table 3 will be applied to the primary and sensitivity analyses of PFS.

Table 3: Censoring Rules for Analyses of Progression Free Survival

Туре		PFS-A1		PFS-B1	
Analysis	Primary		Primary		
Radiographic PD per		IRC	Investigator		
Population		ITT		ITT	
Condition	Outcome	Date of Outcome	Outcome	Date of Outcome	
No post-baseline ATA	Censored	Date of randomization	Censored	Date of randomization	
Death	Event	Date of death	Event	Date of death	
Radiographic soft-tissue PD	Event	Date of PD	Event	Date of PD	
Clinical deterioration	NA	NA	NA	NA	
Any systemic non-protocol anti- cancer therapy (NPACT) received on or after randomization date	Censored	Date of last ATA on or prior to initiation of therapy	Censored	Date of last ATA on or prior to initiation of therapy	
Radiation (other than to bone)	Censored	Date of last ATA on or prior to radiation	Censored	Date of last ATA on or prior to radiation	
Surgery impacting soft tissue lesions	Censored	Date of last ATA on or prior to surgery	Censored	Date of last ATA on or prior to surgery	
≥ 2 consecutive missing scheduled ATA immediately prior to rPD or death	Censored	Date of last ATA prior to the missing assessments.	Censored	Date of last ATA prior to the missing assessments.	

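### Imputed end dates for prior anti-cancer therapy and radiation are not capped at randomization, so a pre-study course can be classed as post-randomization; Table 3 does not say whether that class drives PFS censoring

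*SAP*

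**What the plan says.** **Imputation (SAP Appendix A, end-date rule for prior and concomitant medication, radiation and surgery/procedure).**
- Year only: "set month and day to December 31st".
- Month and year: "Set day to last day of the month".
- No year: "If year is missing (or completely missing): do not impute".

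No bound at randomization or first dose follows. The footnote on medication reads "Including prior and concomitant medications, transfusions and Opioid pain medication record". It does not name anti-cancer drugs, but SAP 4.6 sends incomplete medication and therapy dates alike to this appendix. Radiation is named in the rule's own title.

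**Bounds elsewhere in the appendix.** If an imputed diagnosis date falls after consent, the instruction is to "set diagnosis date to the date of informed consent - 1". An imputed study-treatment stop date is held to the day before the next dosing milestone.

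**Classification (SAP 4.6, on imputed dates).** "Concomitant and Subsequent non-radiation anticancer therapies/radiation therapies are defined as those that stop or continue on or after the date of randomization". The opening of SAP Section 6 refers back to 4.6 for its definitions of prior and concomitant therapy.

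**Censoring (SAP 7.1.3, Table 3).** Systemic non-protocol therapy censors PFS if "received on or after randomization date", at the last adequate tumor assessment up to the start of that therapy. The row for radiation other than to bone has no time qualifier. Table 3 does not cite 4.6.

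**Eligibility (Protocol 4.3).** One exclusion reads "The subject has received prior systemic anti-tumor therapy (eg, chemotherapy, biologic modifiers, or anti-angiogenic therapy) within 28 days of randomization". Neighbouring criteria set washouts for kinase inhibitors, hormonal therapy, radiation and radionuclides.

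**The concern.** The end-date rule moves a partial date to the latest day compatible with it. For a treatment that ended before the study, in the same calendar year as randomization, that day is 31 December, which cannot precede randomization. The class in SAP 4.6 turns on the stop date, so the course becomes concomitant or subsequent therapy although eligibility required it to be over. Nothing in 4.6 removes the record, since a therapy may be summarized as prior and as concomitant or subsequent at once.

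The direct stake is the count of post-randomization anti-cancer therapy and radiation by arm (SAP 6.8 and 6.9). SAP 6.9 states that its table supports the efficacy evaluation.

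The conditional stake is the primary endpoint. If Table 3 were programmed from the 4.6 class, the subject would leave the PFS analysis on the day of randomization. SAP 7.2.1 counts only assessments before a PFS censoring event toward best overall response, so the response record would go too.

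**Working it through.** **1. The plan's event count, for scale.** Inputs from SAP 2.3 and 7.1.3: margin 1.58, one-sided alpha 0.025, power 80%, 1:1 allocation, 150 events. By Schoenfeld's formula, assuming a true hazard ratio of 1:

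- events = 4 × (1.960 + 0.842)² / (ln 1.58)² = 150.05;
- power at 150 events = 80.0%.

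The plan's figure is reproduced.

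**2. One record followed through (illustrative dates).** Neck radiation started in March 2014, stop recorded only as 2016, randomization on 15 June 2016.

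- Appendix A: imputed stop = 31 December 2016, which is 199 days after randomization.
- SAP 4.6: the stop is on or after randomization, so the course is concomitant or subsequent.
- Protocol 4.3: the course must have ended at least 28 days before randomization, so the imputed date is impossible for an eligible subject.

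**3. All dates in one year.** Take 2016 (366 days) and every pair of true stop and randomization date with the stop at least 28 days earlier. There are 338 × 339 / 2 = 57,291 pairs. Apply the year-only rule and the 4.6 test:

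| End-date rule | Pairs classed as post-randomization |
|---|---|
| As written | 57,291 of 57,291 (100%) |
| Capped at randomization − 1 | 0 of 57,291 |

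Now let the true stop lie anywhere from 28 to 365 days before randomization, so that some stops fall in the previous calendar year. There are 366 × 338 = 123,708 pairs, and 57,291 / 123,708 = 46% would be misclassified if recorded by year only.

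**4. Month and year known.** Month-end imputation misclassifies 0.1% of same-year pairs with a 28-day washout and 2.8% with a 14-day washout. The 14-day case in Protocol 4.3 is bone radiation, which Table 3 does not censor.

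**5. What Table 3 would do under each reading.**

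| How post-randomization therapy is identified | Result for the record in step 2 |
|---|---|
| Start date on or after randomization | Not censored |
| Subsequent Anti-Cancer Therapy form | Not censored, if the course is recorded only as prior |
| SAP 4.6 stop-date class | Censored; PFS-A2 dates an event in March 2014 |

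Under the third reading no post-randomization assessment precedes the start of therapy. Protocol 9.2.1.2 then falls back to the randomization date, giving PFS of (0 + 1) / 30.4375 = 0.03 months.

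**6. Size under the third reading only.** The documents give no count of such records. Assume 1, 2, 5 or 10 events are lost from 150 and not replaced: power is 79.7%, 79.5%, 78.6% or 77.2%. The analysis waits for 150 events, so the more likely effect is delay or a smaller risk set.

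**The case against.** The strongest reply is that the SAP nowhere says PFS will be censored this way. SAP 4.6 introduces its imputation for medication tables. Table 3 does not refer to 4.6 and dates censoring from the start of therapy. Protocol 9.2.1.2 speaks of subsequent therapy, and Appendix A has a separate start-date rule tied to the Subsequent Anti-Cancer Therapy form. This stands: censoring at randomization is one possible reading, not a stated outcome. It does not close the matter, because Table 3 asks when therapy was received rather than started and leaves its radiation row undated.

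Four further inferences are tempting, and the documents do not support them.

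- **Surgery is misclassified in the same way.** SAP 4.6 gives surgery no stop-date class.
- **Time since last prior therapy becomes negative.** SAP 6.1 and 6.2 do not say whether the start or the stop date is used.
- **Dates missing only the day add materially.** With a 28-day washout they hardly arise (step 4).
- **The number of subjects can be estimated.** Any rate of partial stop dates would be invented. Sites must check washouts before randomization, so these are the dates least likely to lack a month.

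It is also fair that partial pre-study dates are a baseline feature and should not favour an arm in a blinded randomized trial. SAP Section 11 provides data validation and a review meeting before database lock, which could catch an impossible date, though no such check is named. The footnote leaves some doubt over systemic drugs; for radiation there is none.

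**Conclusion.** The point holds as a defect in the date rules and an ambiguity in the censoring table. A year-only stop in the year of randomization is always misclassified under SAP 4.6. For radiation this follows from the text directly; for anti-cancer drugs it rests on 4.6 sending therapy dates to Appendix A. The tables in SAP 6.8 and 6.9 can be wrong as a result.

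A reader might infer that affected subjects necessarily lose their PFS record. The documents do not support that: it follows only if Table 3 is programmed from the 4.6 class, and the SAP does not specify the source. On that reading the impossible PFS-A2 event date shows that the rules do not fit together.

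The number of affected records is unknown and probably very small, and no appreciable effect on the non-inferiority conclusion should be expected. The case for acting is that a censoring rule for the primary endpoint should not depend on a programming choice when the correction is this cheap.

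**What to change.** 1. **Appendix A, end-date rule.** Add: for anti-cancer therapy and radiation recorded as prior to the study, if the imputed end date is on or after randomization, set it to the date of randomization − 1. Complete dates stay as recorded, so a documented continuation past randomization still shows.
2. **Table 3.** State that the censoring conditions apply to systemic therapy, radiation other than to bone, and surgery affecting soft-tissue lesions with a start date on or after randomization. Appendix A imputes partial prior start dates backward, to 1 January or the first of the month, so this criterion cannot carry a pre-study course past randomization.

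The cost is two sentences in the SAP and one line in the imputation program, with no new data. SAP 4.8 allows clarifications and minor corrections by addendum before unblinding.

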#### 8 SAFETY

## 8.1 Adverse Events and Laboratory Abnormalities

An AE is any untoward medical occurrence in a patient or clinical investigation subject who has been enrolled in a clinical study and who may have been administered an investigational product, regardless of whether or not the event is assessed as related to the study treatment. An AE can therefore be any unfavorable and unintended sign (including an abnormal laboratory finding), symptom, or disease temporally associated with the use of an investigational product, regardless of whether or not the event is assessed as related to the investigational product. Preexisting medical conditions that worsen during a study should be recorded as AEs. Abnormal laboratory values, ECG findings, or vital signs are to be recorded as AEs if they meet the criteria described in Section 8.3.

All untoward events that occur after informed consent through 30 days after the date of the decision to discontinue study treatment are to be recorded by the investigational site. At each scheduled and unscheduled visit, AEs are to be identified and assessed based upon study procedures, routine and symptom-directed clinical investigations, and subject query/report.

Assessment of the relationship of the AE to the study treatment by the investigator will be based on the following two definitions:

- Not Related: An event is assessed as not related to study treatment if it is attributable to another cause and/or if there is no evidence to support a causal relationship.
- Related: An event is assessed as related to study treatment when there is a reasonable possibility that the study treatment caused the event. Reasonable possibility means there is evidence to suggest a causal relationship between the drug and the event. This event is called a suspected adverse reaction. A suspected adverse reaction implies a lesser degree of certainty about causality than adverse reaction, which means any adverse event caused by a drug.

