8.1 Adverse Events

Adverse event terms recorded on the CRF will be mapped to preferred terms (PTs) and system organ class (SOC) using the Medical Dictionary for Regulatory Activities (MedDRA). The severity of AEs will be evaluated by the investigator per CTCAE v4.0 (Cancer Terminology Criteria for Adverse Events) guidelines. The investigator will also judge each event to be "not related" or "related" to study treatment.

A TEAE is defined as any AE with an onset date on or after the date of the first dose of study treatment or any ongoing event on the date of the first dose of study treatment that worsens in severity after the date of the first dose of study treatment.

The end of the AE observation period is defined as the earliest of 30 days after the date of the decision to permanently discontinue study treatment, date of death, consent withdrawal date, data cutoff date and lost to follow up date.

For the purpose of calculating treatment emergence and inclusion in summary tables, incomplete onset dates will be imputed as detailed in Appendix A.

For AE reporting, percentages $\geq 10\%$ will generally be presented as integers, those < 10% will be presented with 1 decimal place (e.g. X.X%). Rounding rules are provided in Appendix B. Calculations based upon percentages will be based upon original unrounded values.

Overview of AE

An overall summary of TEAEs through end of AE observation period (unless indicated otherwise) will be provided with the number and percent of subjects who experienced the following in each treatment group:

- Subjects with a TEAE
- Subjects with a Related TEAE
- Subjects with a Serious TEAE
- Subjects with a Serious Related TEAE at any time
- Subjects with a Worst Grade 3 or 4 TEAE
- Subjects with a Worst Grade 3 or 4 Related TEAE
- Subjects with a Worst Grade 4 TEAE

- Subjects with a Worst Grade 4 Related TEAE
- Subjects with a Grade 5 TEAE on or after first dose date
- Subjects with a Grade 5 TEAE
 - o Subjects with a Grade 5 TEAE \leq 30 days after the last dose of the study treatment
 - Subjects with a Grade 5 AE judged not to be causally related to PD that occurred ≤
 30 days after last dose of the study treatment
 - o Subjects with a Grade 5 AE >30 days after the last dose of the study treatment
 - Subjects with a Grade 5 AE judged not to be causally related to PD that occurred >30 days after last dose of the study treatment
- Subjects with a Related Grade 5 TEAE at any time
- Subjects with a Related Grade 5 TEAE

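### For adverse events with an incomplete onset date, SAP Appendix A ignores the stop date, so an event known to have ended before first dose is classed as treatment-emergent

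*SAP*

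**What the plan says.** The rule for incomplete adverse-event onset dates in SAP Appendix A opens with a scope line, "Assumption: For on-study Adverse Events". It then assigns the first-dose date in four situations:

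- No year: "If *year* is missing (or completely missing): set to the date of first dose".
- Month missing, year known: "If *year* = year of first dose: set the date to the first dose date".
- Only the day missing, year equal to that of first dose: "If *month* = month of first dose: set *day* to day of first dose".
- Residual: "For all other cases: set to date of first dose".

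Other branches keep an earlier onset before dosing, for example "If *month* < month of first dose: set *day* to last day of *month". No branch mentions the stop date.

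SAP 8.1 states that "A TEAE is defined as any AE with an onset date on or after the date of the first dose of study treatment", and says that the Appendix A imputation is applied when treatment emergence is determined. Its second limb covers only events still ongoing at first dose that later worsen. Protocol 9.4.1 counts an event as treatment-emergent if it starts or worsens on or after the first-dose date.

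Collection begins before dosing. Protocol 8.1 requires sites to record "All untoward events that occur after informed consent through 30 days after the date of the decision to discontinue study treatment", and protocol 5.1 allows consent more than 28 days before randomization. The adverse-event listings in SAP 8.1 show both start and stop, so the stop date is available.

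**The concern.** A known stop date before first dose settles the matter: the event cannot have begun on or after first dose, and it was not ongoing to worsen. The written rule disregards that evidence and gives the event an onset later than its own end. It then enters the TEAE summaries and, where the term qualifies, the event-of-interest comparison in SAP 8.3.

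Tolerability is the reason for testing the lower dose (protocol 1.5.1 and 1.5.5), so the TEAE tables should not contain events documented as over before treatment. Such events are plausible. Subjects without RET or RAS documentation may need a screening biopsy, and a minor bleed that resolves before dosing, with only month and year recorded, would be counted as treatment-emergent hemorrhage.

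The omission also stands out within Appendix A. Diagnosis, study-treatment, subsequent-therapy and death dates are each bounded by a known reference date. Adverse-event onset is not bounded by its own stop date.

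**Working it through.** The plan gives no figure to reproduce. The check applies the rule as written to test records.

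**Inputs.** Appendix A onset rule; SAP 8.1 criterion (onset on or after first dose). Illustrative first dose: 20 March 2016. The comparison adds one condition: an event whose stop date is before first dose is not treatment-emergent.

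| Recorded onset | Stop date | Imputed onset | TEAE as written | TEAE with stop check |
|---|---|---|---|---|
| March 2016, day missing | 10 Mar 2016 | 20 Mar 2016 | Yes | No |
| 2016 only | 10 Mar 2016 | 20 Mar 2016 | Yes | No |
| Fully missing | 10 Mar 2016 | 20 Mar 2016 | Yes | No |
| February 2016, day missing | 25 Feb 2016 | 29 Feb 2016 | No | No |
| 2015 only | 30 Dec 2015 | 31 Dec 2015 | No | No |
| 5 Mar 2016, complete | 10 Mar 2016 | 5 Mar 2016 | No | No |

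In the first three rows the imputed onset is 20 − 10 = 10 days after the event ended. The last three rows mark the limits: complete dates, and partial dates in an earlier month or year, are not counted as TEAEs.

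**Does the scope line exclude these events?** No. Protocol 6.5.1 describes adverse-event monitoring while on study as starting at signature of consent, and the rule has its own branches for onsets before first dose.

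**Size per subject.** Planned arm size is 188/2 = 94, so one subject is 1/94 = 1.06 percentage points. At the permitted maximum, 250/2 = 125 and 1/125 = 0.80 points. These are upper limits: a subject who also has a genuine treatment-emergent event in the same summary row is already counted there.

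**How often the branches could apply.** This needs an assumption. Suppose pre-dose onsets are spread evenly over 28 to 31 days before first dose (the 28-day screening window plus up to 3 days from randomization to dosing). Averaged over first-dose dates from 2015 to 2018, 52% (28 days) to 48% (31 days) of pre-dose days fall in the calendar month of first dose, and about 96% in the same year. These shares show that the branches are not remote. They do not say how often onset dates are partial, and the documents do not either, so the number of misclassified events cannot be computed.

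**The case against.** Four points on the other side carry some weight.

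- SAP 4.5 starts the safety observation period at first dose and generally limits summaries to data reported within it. An event reported and resolved in screening arguably falls outside. But the wording is general and yields to other specifications, SAP 8.1 has its own TEAE definition, and the imputed onset lies inside the period. It may reduce the number of records; it does not override the rule.
- Protocol 5.5.2 puts conditions present before first dose on a CRF and speaks of adverse events for findings after first dose. This may also reduce pre-dose records, though protocol 8.1 still requires recording from consent.
- SAP 11 plans validation programs, discrepancy management and a review meeting before lock. A partial onset with a known stop is an ordinary site query, but an unknown day cannot always be recovered, and none of this is a stop-date rule.
- The affected set is narrow, and exclusion criterion 8c, which requires a core biopsy to have healed at least 7 days before randomization, makes the bleeding example less likely, though not impossible.

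A reader might infer more than the documents support:

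- *That the Table 4 flag for Grade 3-4 events (2% or more) would be tripped.* The flag is a between-arm difference by preferred term. Reaching 2/94 = 2.1% needs two such events with the same term in one arm and none in the other. Nothing in the plan suggests that clustering.
- *That the dose contrast is diluted.* Adding the same proportion p to arms with incidences a and b leaves the difference unchanged: (a + p) − (b + p) = a − b. Ratio measures would move toward 1, by an amount that cannot be estimated without the count.
- *That negative durations would distort a table.* No summary of adverse-event duration is planned.
- *That these events would be reported as drug-related.* Relatedness is judged separately by the investigator.

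**Conclusion.** The point holds for adverse events with an incomplete onset date only, and among those only where one of the four branches assigns the first-dose date and the stop date is known to precede first dose. For those records the plan specifies a wrong classification, contrary to protocol 9.4.1.

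The consequence is minor. The count is not in the documents; that it is very small is a judgment, based on how many conditions must coincide. Each affected subject adds up to about 1.1 points to one arm's TEAE incidence at 94 per arm (0.8 at 125). The rule is identical in both blinded arms. PFS and ORR are untouched, protocol 9.4 plans no formal safety comparison, and SAP 8 calls any such comparison exploratory. This is a worthwhile correction to the specification. It is not a threat to the trial's conclusions.

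**What to change.** Add to the onset rule in SAP Appendix A:

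> If the AE stop date is known and is earlier than the imputed onset, set the onset to the stop date. If a complete or partial stop date falls wholly before first dose, the event is not treatment-emergent. Impute to the first-dose date only when the stop date is missing, or could be on or after first dose.

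The cost is this short text and a small programming change using a field already in the listings. Data collection and conduct do not change. SAP 4.8 allows minor corrections of this kind in an addendum approved before unblinding.
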